2.4.3 Rationale for Efficacy Endpoints

2.4.3.1 Patency as the Endpoint of Interest

Efficacy in the setting of vascular access in hemodialysis patients is usually focused on the usability of the conduit (patency), and on the interventions needed to maintain patency over time. Patency may be primary or secondary ([Sidawy 2002](#)). Primary Patency allows no interventions; Secondary Patency allows multiple interventions. To fully understand the utility of the HAV relative to commonly used commercially available ePTFE grafts, it is important to assess both Primary and Secondary Patency as well as the number and types of interventions used to maintain patency.

In this clinical setting, efficacy is usually analyzed by a comparison of survival curves (Kaplan-Meier Plots) – time to loss of patency, with, typically, presentation of the percent patency at fixed timepoints (usually at 6, 12, 18 and 24 months after implantation) ([Dixon 2009](#), [Huber 2003](#), [Dember 2008](#), [Shemesh 2015](#)).

The biological evolution of the HAV as it is populated with cells from the subject is critical to understanding the potential advantages of the HAV, such as fewer access-related infections and longer sustained patency. However, because this evolution takes time, it is likely that early events (i.e., early thrombosis) will not be modulated significantly by the host cells that migrate into the HAV. Instead, the inherent biological properties of the HAV are more likely to translate into longer term patency – best described by Secondary Patency, which is very influenced by development of intimal hyperplasia. Furthermore, Secondary Patency (i.e., a lack of

abandonment) is a better measure of the need for a replacement conduit and protection from unnecessary utilization of anatomical sites for potential future access placement. Access placement should always start as distally as possible, ideally at the wrist and then move more proximally. Once a particular location has been used and failed it is virtually impossible to place an access more distally since the outflow vein will almost always have been compromised. Thus, in patients who have already had one or more accesses in the upper limbs the available sites become limited. It is therefore worth maintaining an existing access as long as possible – even if this requires multiple interventions – rather than to abandon that access site and move on to a new site ([National Kidney Foundation 2006](#)).

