2.4.3.5 Controlling against Bias

This is an open-label, comparative study. It is not possible to blind the investigators or study subjects. Study endpoints (see [Section 4.2](#)) will be determined by the clinical decisions of the investigators (except as noted below for study conduit revisions and access-related infections). To reduce the potential for bias the Clinical Events Committee (CEC) (as described in [Section 9.6.2](#)) will:

- Prospectively provide to study sites a set of clinical guidelines for study conduit interventions and abandonment.
- Review study conduit interventions and abandonment in a blinded fashion to assess compliance with these guidelines.
 - Assessments by the CEC of the appropriateness of interventions will be provided to the DMC by the CEC Coordinator (an employee of the CRO with no other study-related responsibilities). As part of their oversight of study conduct, the DMC will review the pattern of interventions and abandonments between treatment groups overall and by study site to assess whether the management of access complications is similar in the two treatment groups.
- Adjudicate study conduit revisions to determine whether the original study conduit was still being used for dialysis.
- Adjudicate access-related infections using the Centers for Disease Control and Prevention (CDC) definitions for dialysis-associated infections ([CDC 2013](#)).

The outcome of these adjudications (i.e., those involving study conduit revisions and access-related infections) will be used as endpoints in the trial rather than the investigator determinations. All other study endpoints will be based on the clinical decisions of the investigators.

Additionally, across-study cumulative event rates overall and by study arm will not be available to staff involved in the management of the study or study subject care.

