4.2.2 Secondary Endpoints

4.2.2.1 Key Secondary Endpoints:

Efficacy

Time to loss of Primary Patency from implantation

- Defined as 'the interval from the time of access placement until any intervention designed to maintain or reestablish patency, access thrombosis or the measurement of patency', i.e., patent without interventions ([Sidawy 2002](#)).

Safety

Access-related infections ([CDC 2013](#))

4.2.2.2 Other Secondary Endpoints:

Efficacy

1. Rate of interventions required to achieve/maintain Secondary Patency
2. Time to loss of Primary Assisted Patency from implantation
 - a. Defined as 'the interval from the time of access placement until access thrombosis or the time of measurement of patency, including intervening manipulations (surgical or endovascular interventions) designed to maintain the functionality of patent access' i.e., patent without an intervention to clear a thrombus ([Sidawy 2002](#)).
3. Histopathological remodeling of any study conduit (based on any samples collected).
4. The efficiency of dialysis as assessed by $spKt/V_{urea}$ (obtained from dialysis unit for a subset of subjects).

Safety

1. Frequency and severity of AEs
2. Study conduit dilatation:
 - a. True aneurysm formation (conduit lumen diameter > 9 mm)
 - b. Pseudo-aneurysm formation
3. Study conduit spontaneous rupture
4. Anastomotic bleeding or spontaneous rupture

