9.6.2 Clinical Events Committee

A Clinical Events Committee (CEC) will be established to do the following:

- Prospectively provide to study sites a set of clinical guidelines for study conduit interventions and abandonment.
- Review study conduit interventions and abandonment in a blinded fashion to assess compliance with provided guidelines. Assessments by the CEC will be provided to the DMC by the CEC Coordinator (an employee of the CRO with no other study-related responsibilities).
- Adjudicate study conduit revisions to determine whether the original study conduit was still being used for dialysis.
- Adjudicate access-related infections using the Centers for Disease Control and Prevention (CDC) definitions for dialysis-associated infections ([CDC 2013](#)).

The outcome of these adjudications (i.e., those involving study conduit revisions and access-related infections) will be used as endpoints in the trial rather than the investigator determinations. All other study endpoints will be based on the clinical decisions of the investigators.

The CEC will consist of individuals who are not directly involved in the conduct of the study. A separate charter will be established that will describe the roles and responsibilities of the CEC.

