10.3.2 Primary Efficacy Analysis

The primary efficacy endpoint is the time to loss of Secondary Patency.

Study endpoints (see [Section 4.2](#)) will be determined by the clinical decisions of the investigators except for the following events that will be adjudicated by the CEC:

- Study conduit revisions to determine whether the original study conduit was still being used for dialysis.
- Access-related infections using the Centers for Disease Control and Prevention (CDC) definitions for dialysis-associated infections ([CDC 2013](#)).

The outcome of these adjudications will be used as endpoints in the trial rather than the investigator determinations.

The primary analysis will be a non-inferiority analysis, which will be conducted when all subjects are at least 18 months post-implantation.

The primary analysis will be in the ITT population with confirmatory analyses in the mITT and PP populations.

The following rules will apply to the ITT population:

- Subjects in whom the wrong study conduit was implanted (e.g., an HAV implanted in a subject randomized to an ePTFE graft) will be analyzed within their randomized group rather than in their 'implanted' group.
- Subjects in whom no study conduit was implanted will be considered as if abandoned on Day 0 and included in their randomized group.

The hazard ratio (HAV relative to ePTFE) will be estimated using a Cox proportional hazards regression model with treatment group and the randomization stratification variable as factors. Based on the estimated 18-month event-free rate in the ePTFE arm, the non-inferiority margin will be determined by the hazard ratio corresponding to a difference of 10 percentage points. If the lower limit of the two-sided 95% confidence interval for the hazard ratio is greater than the corresponding non-inferiority bound, then non-inferiority will be demonstrated.

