### 2.2.2. Secondary Endpoints

#### 2.2.0.1 ***Key Secondary Efficacy Endpoint***

Time to loss of Primary Patency from implantation. Primary Patency is defined as ‘the interval from the time of access placement until any intervention designed to maintain or reestablish patency, access thrombosis or the time of measurement of patency’, i.e., patent without interventions ([Sidawy 2002](#)).

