### Controlling against bias

This is an open-label, comparative study. It is not possible to blind the investigators or study subjects. Study endpoints will be determined by the clinical decisions of the investigators (except for study conduit revisions and access-related infections). To reduce the potential for bias a Clinical Events Committee (CEC) will:

- Prospectively provide to study sites a set of clinical guidelines for study conduit interventions and abandonment.
- Review individual study conduit interventions and abandonment in a blinded fashion to assess compliance with these guidelines.

- Adjudicate study conduit revisions to determine whether the original study conduit was still being used for dialysis.
- Adjudicate access-related infections using the Centers for Disease Control and Prevention (CDC) definitions for dialysis-associated infections (CDC 2013).

The outcome of these adjudications (i.e., those involving study conduit revisions and access-related infections) will be used as endpoints in the trial rather than the investigator determinations. All other study endpoints will be based on the clinical decisions of the investigators.

Additionally, cumulative event rates overall and by study arm will not be available to staff involved in the management of the study or study subject care.

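### Whether an intervention ends Primary Patency depends on its purpose, which unblinded investigators judge; the blinded review of interventions does not feed the endpoint, and no planned analysis removes that judgment

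*Protocol*

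**What the plan says.** Protocol 4.2.2 measures Primary Patency from access placement "until any intervention designed to maintain or reestablish patency, access thrombosis or the measurement of patency". SAP 2.2.0.1 has nearly the same words: "until any intervention designed to maintain or reestablish patency, access thrombosis or the time of measurement of patency". Neither document lists the procedures that qualify or says how purpose is to be judged. Protocol 2.4.3.1 puts it more briefly: "Primary Patency allows no interventions; Secondary Patency allows multiple interventions".

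On who decides, Protocol 2.4.3.5 states: "It is not possible to blind the investigators or study subjects". The CEC's finding replaces the investigator's for two things only: whether a revised conduit is still in use for dialysis, and access-related infection. For the rest, "All other study endpoints will be based on the clinical decisions of the investigators". Protocol 10.3.2 repeats this in the analysis section: endpoints "will be determined by the clinical decisions of the investigators except for the following events that will be adjudicated by the CEC", followed by the same two items.

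The CEC also has a task that covers interventions. Protocol 9.6.2: "Review study conduit interventions and abandonment in a blinded fashion to assess compliance with provided guidelines". The SAP (Controlling against bias) says: "Review individual study conduit interventions and abandonment in a blinded fashion to assess compliance with these guidelines". Under the protocol these assessments go to the Data Monitoring Committee (DMC). Nothing sends them into the endpoint.

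Protocol 10.3.3 and SAP 6.2 place non-inferiority and superiority on Primary Patency third and fourth in the fixed sequence, after non-inferiority and superiority on Secondary Patency.

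**The concern.** A procedure on the conduit for steal, infection or pseudo-aneurysm is not a loss of Primary Patency if it was not aimed at patency. Leaving it out is then correct under the definition. The difficulty is the borderline procedure, where someone who knows the arm decides what it was for. If those decisions lean differently in the two arms, losses are dropped or added in one arm, and the Cox hazard ratio moves for reasons unrelated to the conduits.

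Two tests could carry a confirmatory claim on this endpoint. The five sensitivity analyses in SAP 6.3 vary the exclusion of one site and the handling of death, transplant, loss to follow-up and withdrawal. None varies which interventions count as loss.

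**Working it through.** **The plan's own figure.** Protocol 10.5 assumes 6-month Primary Patency of 50% (ePTFE) and 55% (HAV), with 350 subjects, 1:1 allocation, 16 months' enrolment and 12 months' follow-up. SAP 11 gives the 10-point margin, and SAP 6.1 converts it to a hazard ratio (HR): ln(0.40)/ln(0.50) = 1.322. The assumed HR is ln(0.55)/ln(0.50) = 0.8625. With exponential times and uniform accrual, 303.6 events are expected. Power = Φ(√(303.6/4) × ln(1.322/0.8625) − 1.96) = 96.1%. With HAV at 53%, 306.4 events give 89.5%. If everyone is followed for exactly 12 months, the figures are 92.5% and 83.7%. The stated power (above 90% and above 80%) is reproduced either way, and this point does not change it.

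**Precision at the current analysis.** I take 175 per arm, 16 months' enrolment and at least 18 months' follow-up (Protocol 10.3.2), so 18 to 34 months. Deaths are censored at about 20% a year (SAP 6.1).
- ePTFE hazard λ = −ln(0.5)/6 = 0.1155 per month. HAV at the margin: 0.1155 × 1.322 = 0.1527.
- Death hazard δ = −ln(0.8)/12 = 0.0186 per month.
- P(event) = λ/(λ+δ) × [1 − (e^(−18(λ+δ)) − e^(−34(λ+δ))) / (16(λ+δ))] = 0.830 and 0.878, or about 145 and 154 events.
- SE of log HR = √(1/145 + 1/154) = 0.116.

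**Illustration of differential labelling.** Suppose a share q of one arm's hazard is left uncounted because of the purpose label, and none of the other arm's. The observed log HR shifts by ln(1−q) if HAV losses are dropped, and by −ln(1−q) if ePTFE losses are. At a true HR equal to the margin, the chance of passing non-inferiority is Φ(∓ln(1−q)/SE − 1.96).

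| q (assumed) | −ln(1−q)/SE | HAV losses dropped | ePTFE losses dropped |
|---|---|---|---|
| 0 | 0 | 2.5% | 2.5% |
| 3% | 0.263 | 4.5% | 1.3% |
| 5% | 0.443 | 6.5% | 0.8% |
| 10% | 0.911 | 14.7% | 0.2% |

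SAP 6.1 takes the margin from the 18-month ePTFE rate. If 50% at 6 months continued exponentially, that rate would be 0.5³ = 12.5% and the margin ln(0.025)/ln(0.125) = 1.774. The 5% row stays at 6.5% and 0.8%. For superiority at a true HR of 1, SE = √(2/145) = 0.117, and dropping 5% of HAV losses gives Φ(0.0513/0.117 − 1.96) = 6.4% for a false finding in favour of HAV.

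The margin is held fixed here. Because the SAP computes it from the ePTFE estimate, dropped ePTFE losses would also move it. The probabilities are not conditional on the two earlier tests having passed.

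**What the documents say about q and its direction.** They give no figure for q. Their one hint about imbalance is the expectation of fewer infections with HAV (Protocol 2.4.3.1 and 2.5.2). That would put more non-patency procedures in the ePTFE arm, so excluding them would raise the HR and work against HAV.

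**The case against.** The case for leaving the plan alone is substantial.

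- The definition is taken from a cited reporting standard, and thrombosis ends Primary Patency without any judgment of purpose. Protocol 2.4.3.2 describes thrombosis as the final step in all graft failures, so the contested subset may be small.
- Purpose is documented at the time. Protocol 8.3.9 requires surgical notes, with the reason for any intervention, within 48 hours, and 8.3.5 requires reasons for procedures in the eCRF.
- The CEC issues guidelines, and the DMC compares intervention patterns by arm and site.
- SAP 6.2 analyses thrombectomies, angioplasties and revisions separately. The SAP section on other events of special interest tabulates steal, thrombosis, stenosis and bleeding requiring intervention. A marked imbalance could show there.
- The CEC charter is a separate document and may ask for more than the protocol states.

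All of this stands, and it limits the weight of the point. It does not close the gap. The guidelines and the DMC review address whether management is similar, not whether a given procedure is counted. The tables describe procedures and events, but none re-tests time to loss of Primary Patency.

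A reader might also see a contradiction between 2.4.3.1 and 4.2.2. The sentence in 2.4.3.1 follows a reference to interventions that maintain patency, and the definition itself carries a similar gloss, so it reads as shorthand. It needs tidying and no more.

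**Conclusion.** The point holds as a gap in endpoint ascertainment that is cheap to close. The intervention component of Primary Patency rests on a judgment of purpose by unblinded investigators. A blinded review of interventions exists but does not inform the endpoint, and no planned analysis tests Primary Patency without that judgment.

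The size cannot be derived from the documents. On assumed values, a 5% differential takes false non-inferiority from 2.5% to about 6.5% or to about 0.8%, depending on the arm that loses events. This rests on exponential event times, the planning rates, a fixed margin and a q that is purely assumed.

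A reader might infer three stronger things that the documents do not support:
- That the bias favours HAV. They show no mislabelling, and their only hint about imbalance points the other way.
- That the endpoint is confirmatory without condition. It becomes so only after two earlier passes.
- That the CEC is stated to read every intervention. The text refers to study conduit interventions. It gives no sampling rule or exception, but it does not say every one.

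**What to change.** 1. In SAP 6.3, add a sensitivity analysis in both arms. The first thrombosis, thrombectomy, angioplasty, stenting or revision of the study conduit counts as loss of Primary Patency, whatever its stated purpose. These categories are already collected under Protocol 4.2.3. The analysis tests robustness and does not replace the main estimate, since it also counts procedures that the definition rightly leaves out.
2. In Protocol 2.4.3.5 and 9.6.2 and SAP 3.2, have the CEC record, within its existing blinded review and from the surgical notes already collected, whether each intervention was directed at patency. State that this label determines the endpoint.
3. Align the shorthand in Protocol 2.4.3.1 with the definition in 4.2.2.1.

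Item 1 costs one re-run of the planned Cox model. Item 2 costs CEC time, including re-reading past interventions, and an amendment to the charter and protocol. Both should be specified before Primary Patency results by arm are seen, or else reported as post hoc.

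Two limits remain. The CEC would judge purpose largely from notes written by unblinded investigators. And no label removes bias in the decision to intervene, which only the guidelines and the DMC review address.

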4.2.3 Events of Special Interest

Events of Special Interest related to interventions and infections will be evaluated and include the following:

- Study conduit abandonment
- Thrombosis / thrombectomy
- Angioplasty or stenting
- Access-related infection

- Pseudo-aneurysm or true aneurysm (conduit lumen diameter >9 mm) formation
- Study conduit spontaneous rupture
 - Iatrogenic injuries are not an Event of Special Interest and should be reported as an AE
- Revision or ligation of the study conduit
- Study conduit removal
- Steal syndrome

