9. SAFETY ASSESSMENTS AND ADVERSE EVENTS

The safety of the HAV and the ePTFE graft will be assessed in terms of the following:

- Anastomotic bleeding or spontaneous rupture
- Conduit dilatation (aneurysm formation [conduit lumen diameter >9 mm] or pseudo-aneurysm)
- Conduit spontaneous rupture
- Conduit infection
- Need for conduit removal
- Access-related bleeding requiring intervention
- Other AEs
- Laboratory parameters (clinical chemistry and hematology)
- Increase from baseline in PRA

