9.4 Reporting of Adverse Events

At each evaluation, the subject will be questioned in a general way and no specific symptoms will be suggested. If any AEs have occurred, they will be recorded on the AE pages of the eCRF and in the subject's medical record. If known, the diagnosis should be recorded in preference to the listing of individual signs and symptoms.

During the Screening period (Day -35 to Day 0 prior to implantation), only SAEs related to study procedures will be reported beginning at the time the subject signs the informed consent form. From Day 0 after implantation to 2 years post-implantation (Month 24 visit) or ET visit, whichever occurs earlier, all AEs will be reported.

During the long-term follow-up period from 2 years to 5 years post-implantation, only the following will be reported by the investigator:

- All SAEs considered related to the HAV
- All Events of Special Interest.

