### **Events of Special Interest other than Access-Related Infections**

Adverse events constituting or leading to events of special interest related to interventions and infections according to Section 2.2.2.5 will be presented descriptively. The analyses will include:

- Aneurysms: incidence rate of clinically significant (requiring intervention) and non-clinically significant (no interventions) aneurysms (100 person-years of retaining secondary patency since implantation) will be reported.

- Pseudo-aneurysms: incidence rate of clinically significant (requiring intervention) and non-clinically significant (no interventions) pseudo-aneurysms (100 person-years of HAV/ePTFE graft use since first cannulation) will be reported.
- Steal syndrome, thrombosis, stenosis, and bleeding of study access: Number and percent of subjects experiencing an event, events by severity, and events requiring interventions by severity will be tabulated by treatment group. Time to onset of first event will be presented descriptively.

All AEs and SAEs will be presented in individual listings. The listing will contain the following information: treatment group, verbatim term, SOC, PT, intensity, relationship to treatment, date and day of onset, date and day of resolution, treatment given to treat the adverse event, the outcome, whether the event was an SAE, whether it led to withdrawal and whether it is a TEAE. Listings will be sorted by subject identification number, non-imputed onset date, SOC, and PT. If the onset date is completely missing, then these events will be presented first. If the onset date is missing a month or a day, then these events will be presented before any complete dates.

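### Bleeding and anastomotic rupture are declared safety outcomes but are not on the Events of Special Interest lists, so their reporting narrows, unequally between arms, after Month 24, while the SAP's bleeding table has no stated time window

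*Protocol*

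**What the plan says.** **Declared outcomes.** Protocol 4.2.2.2 lists "Anastomotic bleeding or spontaneous rupture" as a secondary safety endpoint, separately from rupture of the conduit. SAP 2.2 repeats it. Protocol Section 9 adds "Access-related bleeding requiring intervention" to the safety measures.

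**Events of Special Interest list.** Protocol 4.2.3 opens with "Events of Special Interest related to interventions and infections will be evaluated and include the following". The nine items include "Study conduit spontaneous rupture" and "Revision or ligation of the study conduit", and none names bleeding or the anastomosis. Under the rupture item stands one exclusion: "Iatrogenic injuries are not an Event of Special Interest and should be reported as an AE". The SAP carries the same list (headed 2.2.0.5, cited within the SAP as 2.2.2.5).

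**Reporting windows.** Protocol 9.4 has all adverse events reported to Month 24 or early termination. It then says "During the long-term follow-up period from 2 years to 5 years post-implantation, only the following will be reported by the investigator" and names two categories: serious events attributed to the HAV, and Events of Special Interest. Footnote 10 of Appendix 1 repeats this. Protocol 9.4.1 requires any serious event during the study to be reported and sets no Month 24 limit.

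**Analysis.** The SAP subsection on Events of Special Interest other than infections (7.2.6 in the SAP's revision table) plans "Steal syndrome, thrombosis, stenosis, and bleeding of study access: Number and percent of subjects experiencing an event". It adds breakdowns by severity and by need for intervention, and time to first onset. No time window is given. SAP 1 and 4 plan a final analysis at 60 months.

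**The concern.** Thrombosis and steal syndrome are listed events, and Protocol 8.3.9 has detailed information on listed events collected for five years. Bleeding sits in the same SAP bullet but is not listed. A reader of the 60-month table would reasonably assume that all its rows cover the same period with the same intensity of collection. For bleeding, neither would be so.

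Two features make this more than labelling. The protocol itself regards the outcome as relevant: 2.5.1 names puncture-site bleeding as a risk, 2.4.3.2 names repeated puncture and mechanical damage among the contributors to later failure, and 2.4.3.3 expects differences between HAV and synthetic grafts to appear in the longer term. Also, the late rule for serious events names only the HAV, so a descriptive comparison of late bleeding would compare arms observed under different rules.

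**Working it through.** The plan gives no figure for late bleeding, so there is none to reproduce. The check sets the sections side by side and then sizes the exposed period.

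**1. Where each event stands**

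| Event | Declared in | On the list (4.2.3; SAP 2.2) |
|---|---|---|
| Anastomotic bleeding or rupture | Protocol 4.2.2.2; SAP 2.2 | No |
| Access bleeding needing intervention | Protocol 9 | No |
| Conduit spontaneous rupture | Protocol 4.2.2.2; SAP 2.2 | Yes |
| Thrombosis, steal syndrome | Protocol 4.2.3 | Yes |

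**2. What happens to a bleed after Month 24**

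| Bleed | Route under Protocol 9.4 |
|---|---|
| Leads to revision, ligation, removal, stenting or abandonment (either arm) | Reported through that listed event |
| Serious, HAV arm, judged HAV-related | Reported |
| Serious, HAV arm, judged unrelated, no listed event | None |
| Serious, ePTFE arm, no listed event | None |
| Non-serious, either arm, no listed event | None |

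Read literally, Protocol 9.4.1 would restore the third and fourth rows. The two sections conflict. The fifth row is unaffected by that conflict.

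**3. Whether the late-visit record fills the gap.** Protocol 8.6.1.4 has sites document access problems, procedures and reasons at Months 30 to 60. The Month 2 to 24 visits also have an adverse event assessment (8.5.1.8), and the Month 30 to 60 procedures have no counterpart. The severity scale in Protocol 9.3 is defined for adverse events, and the SAP subsection draws on adverse events. Nothing in the SAP says that the 8.6.1.4 record enters the bleeding table.

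**4. How much conduit time is exposed.** The restricted window is 60 − 24 = 36 of at most 60 months, and applies only to conduits still patent (Protocol 4.3). Inputs:
- 12-month secondary patency of 60% (ePTFE) and 66% (HAV), from Protocol 10.5.
- Annual death rate of about 20%, from SAP 6.1.
- 175 subjects per arm, from the Protocol Summary.
- Exponential loss, which is my assumption.

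Hazards per year: −ln 0.60 = 0.511, −ln 0.66 = 0.416, and death −ln 0.80 = 0.223. Patent conduit-years per subject between years a and b are (e^(−λa) − e^(−λb))/λ.

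| | λ | Years 0–2 | Years 2–5 | Share after Month 24 |
|---|---|---|---|---|
| ePTFE, no deaths | 0.511 | 1.253 | 0.553 | 0.553/1.806 = 30.6% |
| HAV, no deaths | 0.416 | 1.358 | 0.747 | 0.747/2.105 = 35.5% |
| ePTFE, with deaths | 0.734 | 1.049 | 0.279 | 0.279/1.328 = 21.0% |
| HAV, with deaths | 0.639 | 1.129 | 0.372 | 0.372/1.501 = 24.8% |

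With deaths, that is 175 × 0.279 ≈ 49 and 175 × 0.372 ≈ 65 conduit-years. Transplant, withdrawal and the lost site (about 10% of subjects, Protocol 10.5) would lower these further.

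**The case against.** The best defence is that little is lost. Bleeds that end in a listed procedure are reported to Month 60, and Protocol 8.3.9 requires the reason for the intervention. The SAP subsection covers adverse events that constitute or lead to listed events, so a bleed leading to revision is within its scope. HAV-related serious bleeds remain reportable, 9.4.1 may keep all serious events, and 8.6.1.4 keeps a site record. The opening of the list can be read as non-exhaustive. The output is descriptive (Protocol 10.4), so no test depends on it. All of this stands, and it limits the gap to the last three rows of the second table.

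A reader might be tempted to infer more than the documents support:
- **That collection of bleeding stops at Month 24.** It narrows; the routes above continue.
- **That the SAP commits to tabulating bleeding to Month 60.** It states no window. Month 60 is the general timing of the final analysis.
- **That the table would show a false fall in bleeding after year 2.** The specified output is counts, percentages, severity and a descriptive time to first onset. It contains no rate by year.
- **That the SAP has reclassified bleeding as a listed event.** Stenosis stands in the same bullet and is also off the list.
- **That iatrogenic injury should be put on the list.** Leaving it off is an explicit sponsor choice, and reversing it would be a preference.

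What the defence does not answer is that a declared safety outcome has no stated late reporting rule common to both arms. If the list is non-exhaustive, each site decides whether a bleed counts, which is also uneven.

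**Conclusion.** The point holds as a gap between the endpoint list, the reporting rule and the SAP output. If Protocol 9.4 is followed, the bleeding counts at the 60-month analysis would be incomplete after Month 24 and captured by different rules in the two arms.

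The direction of the resulting bias cannot be fixed in advance. Reporting HAV-related serious bleeds without an ePTFE counterpart would work against the HAV. Losing non-serious bleeds would work in its favour if more HAV conduit time falls in the late period.

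The number of missed bleeds is unknown, because the documents give no bleeding rate. The shares of conduit time (21% and 25% with deaths, 30.6% and 35.5% without) describe exposure, not missed events, and rest on the planning rates and exponential loss. Data to Month 24, and the primary efficacy analysis, are not affected. The change should be made, but the matter concerns a descriptive safety table.

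**What to change.** - Add anastomotic bleeding or rupture, and access-related bleeding requiring intervention, to Protocol 4.2.3 and to the SAP's list (2.2.2.5), reported to Month 60 in both arms.
- Reconcile Protocol 9.4 and Appendix 1 footnote 10 with Protocol 9.4.1, so that one rule states which serious events are reported after Month 24 in each arm.
- In SAP 7.2.6, state the time window of the bleeding row. Where late data were not collected, end the row at Month 24 and label it so.

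The cost is a short amendment, two event categories in the eCRF and a few extra event forms. Sites already document access problems at the late visits. The labelling change needs no new data.
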